11. HOW TRUE OR FALSE IS EACH OF THE FOLLOWING STATEMENTS FOR YOU?

a) I seem to get sick a little easier than other people

				
Definitely true	Mostly true	Don't know	Mostly false	Definitely false

b) I am as healthy as anybody I know

				
Definitely true	Mostly true	Don't know	Mostly false	Definitely false

c) I expect my health to get worse

				
Definitely true	Mostly true	Don't know	Mostly false	Definitely false

d) My health is excellent

				
Definitely true	Mostly true	Don't know	Mostly false	Definitely false

SOCIAL SUPPORT

Instructions: This questionnaire requires you to think about current relationships with other participants and/or group leaders in this study. Please read each item and then indicate the extent to which you agree with it by checking one box next to each item with an X.

Some items may seem similar to others, but it is very important that you provide an answer for each item.

1. There are people in this program I can depend on to help me if I really need it.	 Strongly Disagree	 Disagree	 Agree	 Strongly Agree
2. I feel that I do not have close personal relationships with other people in this program.	 Strongly Disagree	 Disagree	 Agree	 Strongly Agree
3. There is no one in this program I can turn to for guidance in times of stress.	 Strongly Disagree	 Disagree	 Agree	 Strongly Agree
4. There are people in this program who depend on me for help.	 Strongly Disagree	 Disagree	 Agree	 Strongly Agree
5. There are people in this program who enjoy the same social activities that I do.	 Strongly Disagree	 Disagree	 Agree	 Strongly Agree
6. Other people in this program do not view me as competent.	 Strongly Disagree	 Disagree	 Agree	 Strongly Agree
7. I feel personally responsible for the well-being of other people in this program.	 Strongly Disagree	 Disagree	 Agree	 Strongly Agree
8. I feel part of a group of people in this program who share my attitudes and beliefs.	 Strongly Disagree	 Disagree	 Agree	 Strongly Agree
9. I do not think other people in this program respect my skills and abilities.	 Strongly Disagree	 Disagree	 Agree	 Strongly Agree
10. If something went wrong, no one in this program would come to my assistance.	 Strongly Disagree	 Disagree	 Agree	 Strongly Agree
11. I have close relationships in this program that provide me with a sense of emotional security and well-being.	 Strongly Disagree	 Disagree	 Agree	 Strongly Agree

12. There is someone in this program I could talk to about important decisions in my life.	 Strongly Disagree	 Disagree	 Agree	 Strongly Agree
13. In this program, people recognize my competencies and skills.	 Strongly Disagree	 Disagree	 Agree	 Strongly Agree
14. There is no one in this program who shares my interests and concerns.	 Strongly Disagree	 Disagree	 Agree	 Strongly Agree
15. There is no one in this program who really relies on me for their well-being.	 Strongly Disagree	 Disagree	 Agree	 Strongly Agree
16. There is a trustworthy person in this program I could turn to for advice if I were having problems.	 Strongly Disagree	 Disagree	 Agree	 Strongly Agree
17. I feel a strong emotional bond with at least one other person in this program.	 Strongly Disagree	 Disagree	 Agree	 Strongly Agree
18. There is no one in this program I can depend on for aid if I really need it.	 Strongly Disagree	 Disagree	 Agree	 Strongly Agree
19. There is no one in this program I feel comfortable talking about problems with.	 Strongly Disagree	 Disagree	 Agree	 Strongly Agree
20. There are people in this program who admire my talents and abilities.	 Strongly Disagree	 Disagree	 Agree	 Strongly Agree
21. I lack a feeling of intimacy with another person in this program.	 Strongly Disagree	 Disagree	 Agree	 Strongly Agree
22. There is no one in this program who likes to do the things I do.	 Strongly Disagree	 Disagree	 Agree	 Strongly Agree
23. There are people in this program I can count on in an emergency.	 Strongly Disagree	 Disagree	 Agree	 Strongly Agree
24. No one in the program needs for me to care for them.	 Strongly Disagree	 Disagree	 Agree	 Strongly Agree

CLINIC ASSESSMENT FORM

1. Is the participant fasting?

1 Yes

2 No

2. Was the fasting blood sample drawn?

1 Yes

2 No

3. Was blood collected for storage and future analysis?

[figure not shown]
1 Yes

[figure not shown]
2 No

Blood Pressure

4. Blood Pressure (after sitting 5 minutes)

1  mm/Hg

2  mm/Hg

AVG  mm/Hg

Body Size

5. Weight . kg

6. Height • cm

[figure not shown]
7. BMI . kg/m²

8. Waist Circumference

ENCOUNTER AND DISPOSITION

1. Was information collected during this visit for a previously missed visit?

Yes

Code for Missed Visit:

		
----------------------	----------------------	----------------------

No

2. Was this visit completed in the clinic as described in the protocol/MOP?

Yes (stop here)

No (complete question 3)

3. Was partial information collected?

Yes

Indicate below the items that were scheduled to be collected but are missing:

Blood draw
 Physical Exam
 Blood Pressure
 Economic Evaluations

HUI-3
 SF-36
 Medications
 IPAQ

FFQ
 Self-Efficacy Qs
 Events Assessment
 Health Behaviors

Why were these not completed as planned?

Phone Contact

Other (specify)

No

Why was this visit missed?

Participant cannot be located
 Participant located but refused clinic visit
 Participant is hospitalized
 Participant died
 Scheduling conflict
 Visit scheduled, but participant did not show

Other (specify)

PRE-SCREENING INTERVIEW

First I would like to collect some general information from you.

What is your name?

Prefix or title preffered: [name]. [name]. Other: _____

First Name	Middle Initial	Last Name	Suffix
Preferred Language:		English ₁	Spanish ₂
Preferred Name			

How did you hear about this study? (check all that apply)

Church Event	1	Newspaper or Magazine Article	7
Community Event	2	Newspaper or Magazine Ad	8
Flyer or Poster	3	Radio Ad	9
Doctor/Doctor's office	4	Television Ad	10
Letter in Mail	5	Don't Know	11
Referral	6	Refused	12
Other (please specify):	13		

1. Has anyone interviewed you or given you information about this study before?

Yes →

When?
 MONTH DAY YEAR

No

Don't Know

2. What is your date of birth?

MONTH DAY YEAR

3. What is your sex?

male

female

4. Which of the following best describes your race?

- 1 African American/ Black
- 2 American Indian/ Native American/ Alaskan Native
- 3 Asian/ Pacific Islander
- 4 White
- 5 Other specify: _____

5. Are you Latino, Hispanic, or of Spanish origin?

- 1 Yes
- 2 No →

PARTICIPANT EXCLUDED

Not Latino, Hispanic, or of Spanish Origin

6. Do you have diabetes?

- 1 Yes →
- 2 No

Are you taking any oral medications or insulin to control your diabetes?

- 1 Yes → **PARTICIPANT EXCLUDED**
- 2 No
- 3 Don't Know

Are you following a special diet or exercise program to manage your diabetes?

- 1 Yes **PARTICIPANT EXCLUDED**
- 2 No

- 4 Borderline →

Are you taking any oral medications?

- 1 Yes → **PARTICIPANT EXCLUDED**
- 2 No
- 3 Don't Know
- 4 Don't Know

7. What is your height?

--	--	--

Feet Inches

***BMI _____ kg/m²

8. What is your weight?

--	--	--

 lbs.

PARTICIPANT EXCLUDED

BMI is not between 23 and 50 kg/m²

9. Have you been diagnosed with or treated for any cancer except (non-melanoma) skin cancer in the last 5 years?

¹ Yes →

PARTICIPANT EXCLUDED

Recent diagnosis and/or treatment of cancer

² No

³ Don't Know

10. Have you ever had any of the following?

your heart stopped and doctors had to restart it with an electric shock or defibrillator

¹ Yes ² No ³ Don't Know

kidney dialysis

¹ Yes ² No ³ Don't Know

implanted defibrillator

¹ Yes ² No ³ Don't Know

major organ transplant

¹ Yes ² No ³ Don't Know

If participant answered yes to any of the above:

PARTICIPANT EXCLUDED
History of major condition/chronic disease

11. Can you walk two blocks (about $\frac{1}{4}$ mile) without stopping without the aid of a cane, crutches, walker or other such device?

¹ Yes

PARTICIPANT EXCLUDED

² No →

Unable to perform moderate intensity exercise

³ Don't Know

12. (If female) Are you currently pregnant or nursing or planning to become pregnant?

¹ Yes →

PARTICIPANT EXCLUDED

² No

Pregnant

³ Male, not applicable

Nursing

Planning pregnancy

13. Have you had any of the following?

Heart Attack

¹ Yes ² No ³ Don't Know

[figure not shown]
Stroke, mini stroke, or TIA

¹ Yes ² No ³ Don't Know

Heart bypass surgery ¹ Yes ² No ³ Don't Know
 Heart angioplasty, balloon surgery
 of the heart, or a stent ¹ Yes ² No ³ Don't Know
 Participated in cardiac rehabilitation ¹ Yes ² No ³ Don't Know

If participant answered yes to any of the above, did it occur in the past six months?

¹ Yes

² No

PARTICIPANT EXCLUDED

Recent history of cardiovascular disease

When was your most recent event?

MONTH

DAY

YEAR

Re-screen 6 months from above date

14. Are you currently taking medications for weight loss or participating in a weight loss program?

¹ Yes

Are you willing to stop taking these medications or
 participating in the other weight loss program for the time
 that you are participating in HELP?

¹ Yes

² No

→ **PARTICIPANT EXCLUDED**

15. Are you currently taking steroid pills or shots such as prednisone or cortisone? (This does not
 include hormone replacement)

¹ Yes

² No

Which ones?

*Contact study doctor for consult before participant can
 continue screening process.*

16. Are you currently being treated for drug or alcohol abuse?

¹ Yes

² No

PARTICIPANT EXCLUDED

Self-Reported substance abuse

17. Have you ever been hospitalized for a major mental disorder or psychiatric problem?

¹ Yes

² No

If "yes", contact study doctor for consult before
 participant can continue screening process.

18. Are you or any members of your household currently participating in any other medical research trials?

¹ Yes

² No

Study:

Contact study coordinator for more information before participant can continue screening process.

19. Are you planning to move from the area in the next 2 years?

¹ Yes

² No

³ Don't Know

PARTICIPANT EXCLUDED

Unable to make time commitment for length of the study

20. Are there times when you might be away for more than 2 weeks at a time that might limit participation in the intervention?

¹ Yes

² No

PARTICIPANT EXCLUDED

Travel may limit participation in intervention

21. Do you know of any reasons, health related or otherwise, that you would not be able to participate completely in a 2 year research study?

¹ Yes

² No

Reason:

Evaluate ability to participate before continuing

If eligible:

Based on these questions, you may be eligible to participate in La Comunidad. We would like to invite you to watch a brief video to learn more about the study. Are you interested in continuing the screening process?

Yes

No

If ineligible:

Based on these questions, it looks like you are not eligible to participate in La Comunidad. We really appreciate your interest in the study and hope that we can contact you in the future for other studies related to diabetes or weight loss. Would it be okay for us to keep your information on file for future studies?

Yes

No

For staff use only

Eligibility status:

Eligible

Ineligible

Refused

Pending: Explain

Call back:

MONTH

DAY

YEAR

5. Was the PAR-Q completed?

Yes

No

Check here if medical clearance is required prior to participation.

6. Measurement of HbA1c

Blood sample collected

. %

Was the HbA1c less than 5.7% or more than 6.5%?

Yes

No

PARTICIPANT EXCLUDED

HbA1c < 5.7% or >6.5%

If ineligible:

Based on the blood that we collected at the screening event, you are not eligible to participate in La Comunidad. This is because your blood sugar was *above/below* the range to qualify for the study. If you would like, please feel free to contact us in the future if you would like to be screened again. We really appreciate your interest in the study and hope that we hear from you again.

Yes

No

Date Participant is scheduled to return:

MONTH

DAY

YEAR

Time: :

AM

PM

Nature of Next Visit:

Additional Screening

Randomization

Current Status:

Eligible

Ineligible

Refused

Contact Information

Complete Legal Name

First Middle

Last Suffix Mother's Name

Address

Address 1

Address 2

City State Zip

Telephone

Home Work

Cell Other

Email

I do not have access to email

What is your preferred contact number?

Home

Work

Cell

Other

What is the best time of day to reach you?

Morning (8 AM-12 PM)

Afternoon (12-5 PM)

Evening (5-8 PM)

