The principles guiding the selection of the following inclusion and exclusion criteria are to ensure the enrollment of participants who meet 3 major criteria: 1) high risk for developing diabetes, 2) no medical contraindications to participate in a lifestyle intervention including unsupervised physical activity and weight loss, and 3) ethical randomization, i.e., there are no compelling reasons that potential participants should be referred for immediate weight loss. Subjects will include 225 overweight or obese adults with pre-diabetes in Forsyth County, NC and the surrounding area. All participants will be required to identify themselves as Hispanic or Latino and we hope to recruit approximately equal numbers of men and women based on their representation in the population of the area. As women are more likely to seek medical care than men, we anticipate at least 50% of our sample to be female. We plan to make concerted efforts to ensure that no less than 40% of our sample is male.

a. Inclusion Criteria

- Demographics: Men and women 18 years of age and older who reside in or near Forsyth County, NC.
- Ethnicity: self-identified as Hispanic or Latino
- Evidence of pre-diabetes: HbA1c of 5.7-6.5%
- Body Mass Index (BMI): 25-45 kg/m²
- Willingness to Accept Randomization: Potential participants must be willing to accept randomization to either the intensive lifestyle intervention or the comparison usual care condition.

b. Exclusion Criteria

- Weight Loss: Currently involved in a supervised program for weight loss.
- Diabetes: Clinical history of diabetes mellitus, or newly diagnosed diabetes mellitus at screening.
- Recent History of Cardiovascular Disease: Clinical history of cardiovascular disease (CVD) occurring within the past 6 months, including myocardial infarction, angina, coronary revascularization, stroke, TIA, carotid revascularization, peripheral arterial disease, congestive heart failure. All persons with recent CVD should be participating in cardiac rehabilitation (with appropriate supervision as indicated) to reduce their risk of recurrence; hence, randomization might raise ethical concerns.

[figure not shown]
- Hypertension: Uncontrolled high blood pressure: BP \geq 160/100. Potential participants can be re-screened after control has been achieved.
- Pregnancy: Pregnancy, breast feeding, or planning pregnancy within 2 years.

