- Other Chronic Conditions: Other chronic disease likely to limit lifespan to less than 2-3 years, including any cancer requiring treatment in past 5 years except non-melanoma skin cancer.
- Medication: Chronic use of medicine known to significantly affect glucose metabolism (e.g., corticosteroids, protease inhibitors).
- Other: Conditions/criteria likely to interfere with participation and acceptance of randomized assignment, including the following: inability/unwillingness to give informed consent, another household member already randomized to La Comunidad, major psychiatric or cognitive problems (schizophrenia, dementia, self-reported active illegal substance or alcohol abuse), participation in another research study that would interfere with La Comunidad.

E. Screening and Randomization

a. Tiered Screening Process

A tiered screening process will be implemented to maximize the efficiency of screening. Interested prospective participants will be identified at the churches, community events, or by advertising, and will complete or be administered an initial pre-screening tool to assess medical history and the diabetes risk screening tool developed by the American Diabetes Association²². If potentially eligible, they will then be invited to take part in an interactive question and answer session to learn more about the study, followed by the informed consent process. Those participants still interested and eligible will then have their height, weight, and blood pressure measured and will complete the physical activity readiness questionnaire (PAR-Q). Those participants who have met all other eligibility criteria will then have a blood draw to determine HbA1c. Figure 2 outlines the screening process that we plan to implement.

Figure 2. Tiered Screening Process for La Comunidad

b. Randomization

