Participants will be recruited to La Comunidad using a mixture of advertising, community recruitment events, and provider referrals from healthcare sites. Given the unique role that churches play in the Latino community, we plan to initiate our recruitment efforts there. Currently, 5 local churches have agreed to serve as partners for this effort and we plan to identify additional churches in the future. We will also request a list of adult patients seen in outpatient primary care clinics at Wake Forest Baptist Medical Center who have no diagnosis of diabetes and for whom ethnicity is recorded as "Hispanic or Latino". This list will be requested from the Enterprise Data Warehouse through the Translational Science Institute and will be used to generate mailings to potential participants. As a part of this data request, we will also request a limited waiver of HIPAA authorization from the IRB and the list generated will only be used under this waiver. We will also plan to post flyers and posters in the Downtown Health Plaza space to supplement these efforts. All flyers, brochures, letters, and other recruitment materials will be submitted to the IRB of Wake Forest University Health Sciences for approval prior to use. Signed informed consent will be obtained from all participants prior to conducting any screening activities. Copies of the signed consent forms will be provided to all participants. The original signed forms will be kept in study files.

We plan to identify local adults who identify themselves as Latino who are at high risk for developing type 2 diabetes. Primary inclusion criteria include BMI of 25-45 kg/m² and evidence of pre-diabetes (based on HbA1c). Candidates will also be screened for co-morbid conditions that would make physical activity unsafe or limit participation in the study, including recent history of an acute cardiovascular disease event, clinical history of diabetes mellitus, cancer or other conditions limiting life expectancy, and major psychiatric or cognitive problems, including depression. For safety purposes, potential participants will also be screened using the Physical Activity Readiness Questionnaire (PAR-Q). Persons who screen positive on the PAR-Q will be required to obtain medical clearance from a physician prior to participation.

VII. Informed Consent

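### Item 6 of the pre-screening form lets some people who report diabetes continue, which does not match the exclusion of a clinical history of diabetes

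*Combined protocol and SAP*

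**What the plan says.** The exclusion list in protocol section III.D.b names "Clinical history of diabetes mellitus, or newly diagnosed diabetes mellitus at screening". It attaches no condition about current treatment. Section VI (Subject Recruitment Methods) says that candidates are screened for several conditions, "including recent history of an acute cardiovascular disease event, clinical history of diabetes mellitus, cancer or other conditions limiting life expectancy", again without a treatment qualifier.

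Section III.E.a (Tiered Screening Process) describes the first step as "an initial pre-screening tool to assess medical history", together with a diabetes risk score. Consent, body measurements, blood pressure, the PAR-Q and finally the HbA1c draw come later.

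The Pre-Screening Interview in Appendix B asks at item 6: "6. Do you have diabetes". A Yes opens two follow-up questions: "Are you taking any oral medications or insulin to control your diabetes" and "Are you following a special diet or exercise program to manage your diabetes". The exclusion label is printed against Yes on each follow-up. None is printed against the Yes to having diabetes, nor against No or Don't Know on the drug question, nor against No on the diet or exercise question. Borderline is a separate answer with its own branch. People who clear the form are told: "Based on these questions, you may be eligible to participate in La Comunidad".

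**The concern.** The criterion turns on whether the person has a history of diabetes. The form turns on whether the person is managing it. Someone who reports diabetes but takes no drug and follows no diet or exercise programme meets the exclusion in section III.D.b if the report reflects a clinical diagnosis, yet nothing on the form stops them.

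The trial concerns prevention of diabetes in people with pre-diabetes, so this criterion helps define its population. Section III.K lists accurate assessment of eligibility among the things on which the trial's integrity depends, and section IX requires the semi-annual reports to address whether all participants met entry criteria. A routing rule that conflicts with a core criterion creates a risk of violations that would be found only after entry.

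**Working it through.** The plan gives no figure on this point, so the check is a count of the printed branches of item 6 against the criterion, followed by a search for any later step that would catch the open branches.

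**Branch count after a Yes to diabetes.** The drug question has 3 answers (Yes, No, Don't Know) and the diet or exercise question has 2 (Yes, No), which gives 3 × 2 = 6 combinations.

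| Drugs or insulin | Diet or exercise programme | Form, item 6 | Section III.D.b, if the diagnosis is clinical |
|---|---|---|---|
| Yes | Yes | excluded | excluded |
| Yes | No | excluded | excluded |
| No | Yes | excluded | excluded |
| Don't Know | Yes | excluded | excluded |
| No | No | continues | excluded |
| Don't Know | No | continues | excluded |

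The form closes 4 of 6 and leaves 6 − 4 = 2 open. If a Yes on drugs ends the item at once, there are 1 + 2 × 2 = 5 paths, of which 3 are closed and the same 2 stay open.

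**Is this a product of the damaged layout?** Some arrows and option numbers in item 6 are out of order in the text available. The exclusion labels nevertheless sit with the follow-up answers, and the follow-ups would serve no purpose if every Yes to diabetes were already excluded. Because Borderline has its own branch, Yes cannot be read as meaning pre-diabetes.

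**How the same form treats other conditions.** Items 9, 10 and 16 exclude on the reported condition itself. Items 15 (steroids) and 17 (psychiatric hospitalization) send a Yes to the study doctor before screening continues, and item 18 sends it to the coordinator. The open branches of item 6 have no such instruction. Item 14 still refers to taking part in HELP, which suggests that the form was carried over from the earlier study.

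**Would a later visible step catch the two open branches?**
- HbA1c: the later screening form excludes only values below 5.7% or above 6.5%. A person inside that range passes.
- Medication review (Table 3): it cannot identify someone who takes no diabetes drug.
- Diabetes risk test: it asks about gestational diabetes and relatives with diabetes, not about the respondent's own diabetes more generally.
- Family history form: it asks about parents and siblings.
- The clinic list restricted to patients without a diabetes diagnosis (section VI): it governs mailings only, not recruits from churches, events or advertising.
- Medical history (section III.H.c and Table 3): the protocol says that diabetes history is obtained during screening in order to apply the criteria. This is the one stated safeguard, but item 6 is the only visible question that would carry it out.

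**The case against.** The best defence is that the form is only a first filter. It accepts a BMI of 23-50 where the protocol requires 25-45, it promises no more than possible eligibility, and it offers staff a pending status. Section III.E.b allows only people who satisfy the criteria to proceed to the baseline visit and randomization, and section III.H.c says that diabetes history will be taken. Fuller procedures belong to the Manual of Procedures, which is not among the documents. Items 1-4 of the later screening form and the screening figure are not shown, so a further question on diabetes may exist. Item 6 also records self-report and does not ask whether a clinician made the diagnosis, so letting an unmanaged report go forward for checking could be deliberate.

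Much of this stands. A reader might infer that people with known diabetes will be randomized, or that nothing later asks about diabetes. The documents support neither: passing the form does not override section III.D.b, and the most that can be said is that no second question is visible. A reader might also infer damage to the primary result, because such people cannot develop the condition being prevented or would start glucose-lowering drugs. The first argument carries little weight, since the primary outcome is change in HbA1c rather than new diabetes. The documents give no support for the second.

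The comparison with BMI does not remove the mismatch. The wide BMI limits do no harm because height and weight are measured afterwards. No corresponding second look at diabetes history is visible. If the intention was to verify unmanaged reports, the form does not say so, although it does say so for items 15 and 17.

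**Conclusion.** The mismatch is real and should be corrected. As printed, item 6 lets two of the six answer combinations after a Yes to diabetes continue without exclusion or referral, while sections III.D.b and VI exclude a clinical history of diabetes without regard to treatment. The HbA1c window would not detect such a person whose value is 5.7-6.5%.

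The number of people affected is unknown. The documents give no rate from which to estimate it, and it could be close to zero. The effect on the HbA1c comparison is probably small, and no effect on power can be computed. The consequence is avoidable eligibility violations.

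This rests on reading item 6 as printed despite its damaged layout, and on the absence of another diabetes question from the forms that can be seen. If items 1-4 of the later form or the Manual of Procedures contain one, the risk to enrolment largely disappears, and what remains is an inconsistent form.

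**What to change.** Reconcile item 6 with sections III.D.b, III.H.c and VI. Any Yes to having diabetes should lead either to exclusion or to a pending status, with a documented check of the diagnosis completed before the HbA1c draw and randomization. The study-doctor referral already used in items 15 and 17 would serve as a model for the pending route. If the Manual of Procedures or the later screening form already contains such a check, item 6 should point to it.

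The cost is one instruction on the form and a few more exclusions or checks at pre-screening. The design, sample size and analysis do not change. If enrolment has begun, the completed forms can be searched for the two open combinations, and any randomized person found can be covered in the next semi-annual report.

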		
City	State	Zip Code

	
Phone Number	Relationship

2.			
	First Name	MI	Last Name

		
Street Address		

		
City	State	Zip Code

	
Phone Number	Relationship

3.			
	First Name	MI	Last Name

		
Street Address		

		
City	State	Zip Code

	
Phone Number	Relationship

B. Please list the name and telephone number of a person within your household.

		
----------------------	----------------------	----------------------

First Name

MI

Last Name

	
----------------------	----------------------

Phone Number

Relationship

Cell Phone Number

Lives Alone

C. What is the name and address of a physician whom you consider to be your regular source of medical care?

		
----------------------	----------------------	----------------------

First Name

MI

Last Name

Name of Practice or Office

Street Address

		
----------------------	----------------------	----------------------

City

State

Zip Code

Phone Number

MEDICATIONS

We are interested in the prescription medications you are using. We are particularly interested in medications your doctor prescribed for you and were filled by a pharmacist. These include pills, skin patches, eye drops, creams, salves, inhalers, and injections. The letter you received about this appointment asked you to bring them to the clinic. Have you brought them with you? Are these all medications that you took in the last two weeks?

 Yes	—————→	May I see them?
 No	—————→	Make arrangement to obtain.
 Took no meds		
 Refused		

1. _____
2. _____
3. _____
4. _____
5. _____
6. _____
7. _____
8. _____
9. _____
10. _____
11. _____
12. _____
13. _____
14. _____
15. _____

SHORT FORM 36

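### The pre-screening form does not match the protocol's medication criteria: its Borderline branch excludes on any oral medicine, and most respondents are asked only about steroids and weight-loss drugs

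*Combined protocol and SAP*

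**What the plan says.** **Protocol criterion.** Section III.D.b excludes "Chronic use of medicine known to significantly affect glucose metabolism (e.g., corticosteroids, protease inhibitors"). The class is open, with two examples. Nothing in III.D.a or III.D.b excludes a person for taking oral medicines in general.

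**Pre-Screening Interview, Appendix B.** Three items touch on medicines:

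- Item 6 (diabetes). After *Yes*, the form asks "Are you taking any oral medications or insulin to control your diabetes" and excludes on a yes. After *Borderline*, it asks "Are you taking any oral medications", with no limit to diabetes or blood sugar, and also excludes on a yes. After *No* or *Don't Know*, no medication question follows.
- Item 14, put to everyone: "Are you currently taking medications for weight loss or participating in a weight loss program". A yes leads to a question about willingness to stop.
- Item 15, put to everyone: "Are you currently taking steroid pills or shots such as prednisone or cortisone". A yes leads to an instruction, "Contact study doctor for consult before participant can" go on, not to automatic exclusion.

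**Later medication capture.** Table 3 schedules a Medication Review at baseline and at every follow-up visit. The Appendix B Medications form opens "We are interested in the prescription medications you are using" and lists the drugs taken in the last two weeks. It carries no eligibility step. Section III.E.b invites people to the baseline visit once they satisfy the criteria, and they are randomised there.

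**The concern.** The form and the criteria disagree in both directions.

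The *Borderline* branch is stricter than the protocol. It bears on people who already know that they have raised blood sugar, the population that the trial is meant to enrol. If staff follow the printed text, some eligible people never reach the HbA1c test, and the sample shifts towards people who are undiagnosed or unmedicated.

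Elsewhere the form is looser than the protocol. A person on an excluded drug other than a steroid can pass pre-screening without being asked, and no later documented step requires the drug list to be compared with the exclusion before randomisation.

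Section III.K treats accurate assessment of eligibility as part of trial integrity, and section IX requires the semi-annual reports to say whether all participants met the entry criteria. For the medication criterion, the form as printed does not supply the information needed.

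**Working it through.** **1. Criterion against form.**

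| Medicine | Section III.D.b | Pre-Screening Interview |
|---|---|---|
| Corticosteroids | Named as excluded (chronic use) | Item 15, everyone; study-doctor consult |
| Protease inhibitors | Named as excluded (chronic use) | No visible item |
| Rest of the open class | Excluded (chronic use) | No general question; item 14 reaches drugs taken for weight loss |
| Glucose-lowering drugs | Covered if they meet the class description | Only after *Yes* or *Borderline* at item 6, apart from item 14 |
| Oral medicines in general | Not excluded | Excluded after *Borderline* |

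The form asks by name about 1 of the 2 classes that the protocol names.

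**2. Does the protocol expect participants on oral medicines?** Yes, in several places.

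- Section III.H.b defines hypertension at baseline partly by antihypertensive use.
- PAR-Q question 6 asks about prescribed blood-pressure or heart drugs. Under section V.B a positive PAR-Q leads to medical clearance, not exclusion.
- Section III.D.b allows people with uncontrolled blood pressure to be re-screened once it is controlled.

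The *Borderline* exclusion, read as printed, conflicts with all three.

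**3. Size of the wrongful exclusion.** The documents give no figure. If a share *q* of otherwise eligible *Borderline* respondents takes an oral medicine that III.D.b does not exclude, the form turns away that share. Assuming *q* = 20–50%, this is 2 to 5 in every 10 such people.

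**4. Size of the effect on the primary comparison.** The documents give no prevalence, so the share of users *f* and the difference *d* in their one-year HbA1c change are assumptions.

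- Number of users: 0.01 × 225 = 2.25 and 0.05 × 225 = 11.25, so about 2 to 11 people.
- Retained at 12 months with 5% loss per 6 months: 225 × 0.95² = 203, or 135.4 and 67.7 under 2:1 allocation.
- Base SD of change, back-solved from the lower stated power (85% for 0.25%): SD = 0.25 / [(1.960 + 1.036) × √(1/67.7 + 1/135.4)] = 0.25 / (2.996 × 0.1489) = 0.56. The protocol does not state this SD.
- With users balanced across arms, the variance becomes 0.56² + *f*(1 − *f*)*d*².

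| *f* | *d* (HbA1c points) | SD | Power |
|---|---|---|---|
| any | 0 (stable use) | 0.560 | 85.0% |
| 1% | 0.25 | 0.561 | 84.9% |
| 5% | 0.25 | 0.563 | 84.7% |
| 5% | 0.50 | 0.571 | 83.7% |
| 10% | 0.50 | 0.580 | 82.5% |

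**5. Could it bias the comparison?** Use that predates randomisation is balanced in expectation. Drug changes after randomisation could differ by arm, because participants and staff are unmasked (section III.A) and the primary model has no covariates (section IV). As an extreme, if 5% of one arm shifted by 0.5 points and nobody in the other did, that arm's mean would move by 0.05 × 0.5 = 0.025, a tenth of the 0.25 target.

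**The case against.** **The form is only the first tier.** Section III.E.a calls for further steps, III.E.b requires all criteria to be met, and staff review prescriptions at baseline. So the protocol governs, and an excluded user may still be caught. This stands in part: the form does not prove that such users are randomised. But no text ties the medication list to eligibility, and no later step recovers someone rejected at pre-screening.

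**Not everything is visible.** The later screening section begins at item 5, and the Manual of Procedures, which holds the enrolment detail (section III.I), is not available. A drug question in items 1–4 cannot be ruled out. It seems unlikely, since III.E.a places consent, height, weight and blood pressure before the PAR-Q and HbA1c, but this limits confidence to moderate.

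**The *Borderline* wording may be shorthand.** It sits under a diabetes question, beside a branch limited to diabetes treatment, and the response codes around it are garbled in the extracted text. That may well be the intent. The question itself is intact, however, and lacks the limit that its neighbour has. Item 14 still names HELP as the study, which suggests a form carried over without full reconciliation.

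**A consult for steroid users is not a fault.** The item asks about current use and the criterion concerns chronic use, so a consult is a reasonable way to separate them. This stands.

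**Conclusion.** Two mismatches hold on the printed text. The *Borderline* branch excludes on a ground that the protocol does not contain, and the medication exclusion is not put to everyone. The consequences are wrongful exclusion of some target participants and possible enrolment of some who do not meet the criteria. The first affects recruitment and generalisability, not internal validity. Both sizes rest on assumed prevalences.

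A reader might infer three stronger things, which the documents do not support:

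- *That most glucose-altering drugs go unasked.* The excluded class is open, so no such share can be counted, and item 14 reaches some of these drugs when they are taken for weight loss.
- *That drug-altered HbA1c materially threatens the primary outcome.* The analysis uses change from baseline in randomised arms. Stable use leaves the change score alone, earlier use is balanced in expectation, and the remaining noise costs about 0.1 to 1.3 percentage points of power under 1–5% use.
- *That a drug effect in one person can be set against the 0.25% target.* The target is a difference in group means; an individual shift must first be multiplied by the share of people affected, as in step 5 of the working.

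The point is worth acting on because the correction is nearly free, not because the primary result is in danger.

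**What to change.** 1. **Item 6, *Borderline* branch.** Reconcile it with section III.D.b: either limit the question to medicines taken for blood sugar, in parallel with the *Yes* branch, or, if a wider exclusion is intended, state it in III.D.b.
2. **Item 15.** Ask everyone, whatever the answer to item 6, about the class that III.D.b excludes, including protease inhibitors. Keep the study-doctor consult for unclear cases.
3. **Baseline visit.** Check the Medications form against III.D.b, and record the result, before the randomisation routine is opened.
4. If items 1–4 of the later screening form or the Manual of Procedures already cover this, a cross-reference in section III.E is enough for steps 2 and 3.

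The cost is two reworded items and one check of a list already collected. A few more people will be excluded for medication, against those no longer turned away. The change does not address drugs started after randomisation; the Medication Review at each follow-up visit already records those.
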